**Name** **Created** **Modified Date**

There are no items to display

8 \* Discuss any other potential confidentiality issues related to this study:

None

ID: V1EW4E1B5265E0400  
Name: v2\_Confidentiality of Data

HP-00081981

Monitoring Plan Selection\_V2

## Monitoring Plan Selection

1 \*Type of data safety monitoring plan for the study:

- Will use/defer to the external sponsor's Data Safety Monitoring Plan
- Data Safety Monitoring by a Committee
- Data Safety Monitoring by an Individual**
- There is no data safety monitoring plan in place

ID: VIEW4E1B00E30D400  
Name: v2\_Monitoring Plan Selection

HP-00081981

Monitoring Plan - Individual\_V2

## Monitoring Plan - Individual

You indicated that the monitoring will be done by an Individual.

1 \* Identify the individual who will be performing the safety monitoring:  
[name]

2 \* Describe this individual's role in relation to the protocol:  
Principal Investigator

3 \* What data will be reviewed?

- Adverse Events
- Enrollment Numbers
- Patient Charts/Clinical Summaries
- Laboratory Tests
- Medical Compliance
- Procedure Reports
- Raw Data
- Outcomes (Primary, Secondary)
- Preliminary Analyses
- Other

3.1 If Other, specify:

4 \* What will be the frequency of the review?

- Annually
- Bi-Annually
- Other

4.1 If Other, specify:

5 \* Safety monitoring results will be reported to:

- IRB
- GCRC
- Sponsor
- Other

5.1 If Other, specify:

HP-00081981

Research Related Costs\_V2

## Research-Related Costs

1 \* Is the study's financial supporter (e.g., commercial sponsor, federal or state grant or contract, private foundation, physician-sponsor) covering any research-related costs?

No  
 Yes

1.1 If Yes, check all that apply:

Research-Related Services (personnel costs, tests, supplies, exams, x-rays, or consultations required in the study)  
 Investigational or Study Device  
 Investigational or Study Drug  
 Investigational Procedure(s)

1.2 If No, who is responsible for payment?

2 \* Who is responsible for the uncovered research-related costs?

Participant  
 Sponsor  
 UM  
 Other  
 There will be no uncovered research-related costs

2.1 If Other, specify:

3 If the participant is responsible for any research-related costs, identify and estimate the dollar amount:

ID: VIEW4E1B5D9641800  
Name: v2\_Research Related Costs

HP-00081981

Compensation for Research Related Injury\_V2

## Compensation for Research-Related Injury

1 \* Is this study under a master agreement that includes a provision requiring the sponsor to provide compensation to participants for research-related injury?

 Yes  No

1.1 If Yes, please provide the date and title of the agreement and upload the portion of the contract language relevant to compensation for research-related injury:

Name	Created	Modified Date
------	---------	---------------

There are no items to display

1.2 If No (the study is not under a master agreement), is there proposed contract language concerning payment to participants for treatment in the event of a research-related injury?

 Yes  No

1.2.1 If Yes, indicate the status of the contract review/approval with the ORD and upload the proposed language relevant to compensation for research-related injury:

Name	Created	Modified Date
------	---------	---------------

There are no items to display

ID: VIEW4E1B629EEC000  
Name: v2\_Compensation for Research-Related Injury

HP-00081981

Payment to Participants\_V2

## Payment/Reimbursement to Participants

1 \* Will participants receive payment (money, gift certificates, coupons, etc.) or reimbursement for their participation in this research?

Yes  No

ID: V1EW4E1C52A5D7800  
Name: v2\_Payment to Participants

HP-00081981

Payment Detail\_V2

## Payment/Reimbursement Detail

You indicated that participants will receive payment (money, gift certificates, coupons, etc.) or reimbursement for their participation in this research.

1 \* Payment/reimbursement to participants will be for: (check all that apply)

- Travel
- Parking
- Meals
- Lodging
- Time and effort
- Other

1.1 If Other, specify:

2 \* What is the total dollar value of the payments/reimbursements over the duration of the study? **Total payment(s) for participation in research of \$600 or more in a calendar year is required to be reported on an IRS Form 1099.**  
up to \$85

3 \* Describe the timing and distribution plan for the payment/reimbursement (schedule, means, etc.)?

Probands will be compensated up to \$85 over the course of the study. Five dollars in cash will be included in each of the two mailed surveys. If a proband participates in an interview, a check in the amount of \$75 will be mailed to them 6-8 weeks after the interview.

Family members will be compensated up to \$85. If a family member participates in an interview, a check in the amount of \$75 will be mailed to them 6-8 weeks after the interview.

Mod 14 - Participants who complete and return the mailed questionnaire will have the option to choose from a listing of 2-3 community-based 501c3 charities to receive a \$5 cash donation as compensation for completing the questionnaire.

4 \* Method(s) of payment/reimbursement to be Used:

- Cash
- Check
- Money Order
- Gift Certificate/Gift Card
- Other

4.1 If Other, specify:

ID: VIEW4E1C54A6ACC00  
Name: v2\_Payment Detail

HP-00081981

HIPAA\_V2

## HIPAA (Health Insurance Portability and Accountability Act)

1 \* Are you affiliated with, or will you be accessing data from a HIPAA-covered entity? A covered entity might be a hospital, a physician practice, or any other provider who transmits health information in electronic form.

- At UMB, this includes UMB schools designated as covered entities (School of Medicine and School of Dentistry) and entities under the University of Maryland Medical System (UMMS). The Baltimore VA Medical Center is also a covered entity.
- If you are a researcher from any school that is not a covered entity but is accessing electronic medical records from a covered entity (such as UMMC), HIPAA would be applicable. Please see a list of covered entities included under UMMS here: [executed-ace-designation-042018.pdf](#)

 Yes  No

2 \* If Yes, will the study view, access, share, collect, use, or analyze health information that is individually identifiable under HIPAA?

 Yes  No

ID: VIEW4E1B0A2114400  
Name: V2\_HIPAA

HP-00081981

Protected Health Information\_V2

## Protected Health Information (PHI)

You indicated that HIPAA applies and the study will view, access, share, collect, use, or analyze health information that is individually identifiable.

1 \* Which PHI elements will be used or disclosed in this study? (Check all that apply)

- Name
- Address (if more specific than Zip Code)
- Dates
- Ages over age 89
- Telephone numbers
- Fax numbers
- Email addresses
- Social Security numbers
- Medical record numbers
- Health plan beneficiary numbers
- Account numbers
- Certificate/license numbers
- Vehicle identifiers and serial numbers, including license plate numbers
- Device identifiers and serial numbers
- Web universal resource locators (URLs)
- Internet protocol (IP) address numbers
- Biometric identifiers, including fingerprints and voiceprints
- Full-face photographic images and any comparable images
- Any other unique identifying number, characteristic, or code, unless otherwise permitted by the Privacy Rule for re-identification
- None

2 \* Why is the PHI necessary for this research?

*If SSNs are going to be used, describe the specific use and type of SSN to be used (real, scrambled, last 4 digits).*

The above noted identifiers are needed to contact participants to offer participation and communicate with participants during the course of study participation; to establish a link between the unique study id and the individual ; and social security numbers are required to obtain participant compensation

3 \* What is the source(s) of the PHI?

Participant and the Fisher Book and Church directory of the Old Order Amish of Lancaster County.

4 \* Provide written assurance that Protected Health Information will not be reused. (Note: this refers to re-use on another study or for a purpose which has not been approved, not to the re-use of screening data during the current study).

The PHI collected from participants will only be used for the uses approved in this protocol. Only subjects who agree to recontact for future studies (see consent form) may be approached to offer participation in other studies.

5 \* How will permission to allow the use/disclosure of the individual's protected health information (PHI) be obtained? (Choose all that apply:)

- Obtain written authorization (*upload authorization form at the end of the application under "Consent and HIPAA Authorization Forms"*)
- Requesting waiver/alteration of authorization (includes waiver of authorization for recruitment only)
- Qualifies as a limited data set (LDS)

5.1 If you are using a limited data set (LDS), please attach the Data Use Agreement (DUA):

**Name****Created****Modified Date**

There are no items to display

*ID: VIEW4E1B0A24AA400  
Name: v2\_Protected Health Information*

HP-00081981

Waiver - Alteration of Authorization\_V2

## Waiver/Alteration of Authorization

You indicated that a waiver/alteration of authorization is requested.

- 1 \* Provide rationale for how the research presents no more than minimal risk to the privacy of individuals:  
We are requesting a waiver of authorization for the survey portion of this research. Completion of the survey, if the individual chooses to do so, represents similar risk to privacy to that which would be encountered in everyday life, for instance, in the context of standard medical care. Moreover, the participant can choose not to respond without any penalty or loss of benefit otherwise entitled.
- 2 \* Describe the plan to ensure the protection of PHI collected during this study from improper use and disclosure:  
All returned surveys will be secured in locked cabinets or locked offices of the study data manager upon receipt. Survey data will be entered in password-protected, secure databases behind the UMSOM firewall. Computers are password protected and located in secure offices. Access to the paper and electronic information is only given to research team members for whom it is essential to their study role or responsibilities.
- 3 \* Describe the plan to destroy the PHI collected during this study at the earliest opportunity consistent with the conduct of the research. If there is a need to retain PHI, provide a justification:  
We will not destroy the PHI collected with the returned questionnaires. We need to retain the family relationship information of the participants completing surveys.
- 4 \* Why could the research not practicably be done without access to and use of this PHI?  
We could not identify and mail questionnaires to participants without access to and use of this PHI.
- 5 \* Why could the research not practicably be done without the waiver or alteration?  
Because the documentation of consent has been waived it would not be practical to include a HIPAA authorization.
- 6 \* Will the subjects' PHI be disclosed to (or shared with) any individuals or entities outside of UM?  
 Yes  No

6.1 If Yes, describe the individuals or entities outside of UM to whom PHI will be disclosed.

ID: VIEW4E1B0A2896400  
Name: v2\_Waiver/Alteration of Authorization

HP-00081981

Informed Consent Process\_V2

## Informed Consent Process

**If the study does not involve interaction with participants or a waiver of consent is being requested , answer "N/A" to the questions below.**

1 \* Indicate the type(s) of consent that will be involved in this study: (check all that apply)

- Not applicable (study may qualify as exempt)
- Request to Waive Consent/Parental Permission (Consent is not being obtained)
- Request to Alter Consent (Some Elements of Consent Waived)
- Request to Waive Documentation of Consent (Verbal/Oral Consent)
- Written Consent Form
- Electronic Consent

2 \* Describe the Informed Consent process in detail:

Family member consent process: Family members will be visited in their home after the ARC staff receives their response card expressing interest in testing, or possibly if no response is received. Participants will be approached by a study team member (usually a nurse) and an Amish liaison. The study will be briefly explained to the participant who will be asked if they would like to hear more about the study for possible participation. If they are unsure, information will be given with the name and phone # of the study team member to contact if they are interested in hearing more in the future. If the potential participant expresses interest in the study and invites the study team into their home, the study will be explained in detail using the consent form. The potential participant will be invited to ask questions throughout the process and will be reminded often that the study is voluntary. Ample time will be given to make a decision regarding participation in the study. If they decide to participate the consent form will be signed and dated by both the participant and the study team member.

We are requesting a Waiver of Documentation of Consent for probands and family members who decline genetic testing. These individuals will be mailed an information / consent letter along with a questionnaire.

3 \* Confirm that the consent process will explain the following:

- The activities involve research.
- The procedures to be performed.
- That participation is voluntary.
- The name and contact information for the investigator.

Yes  No

4 \* Describe who will obtain Informed Consent:

Designated, trained members of the research team will obtain informed consent.

5 \* If obtaining consent from a legally authorized representative (LAR), describe how you will confirm that the individual is the LAR and can provide legally effective informed consent. (Answer "N/A" if not obtaining consent from LARs)  
N/A

6 \* Describe the setting for consent:

Consent obtained in the home is done in private whenever possible. If young children are present and the research volunteer is their caregiver, it is sometimes not feasible to separate the participant from the children to obtain consent. In these cases, with the permission of the research subject, we obtain consent in the presence of the children. Finally, with permission of the research subjects, husbands and wives are sometimes consented together. It is most culturally appropriate to be in the kitchen, dining or living room of the home and inappropriate to use a more private setting such as a bedroom or office. When at all possible, interactions will occur in a corner of the room, away from the activity of the family.

7 \* Describe the provisions for assessing participant understanding:

All participants must be alert, oriented and be able to respond appropriately to questions during and after the consent discussion. The participant will be asked open ended questions about the purpose and risks of the study. Participants will be asked about voluntary nature of participation and what they would do if they wanted to withdraw or if they had an adverse event. If a subject cannot correctly respond to questions about the study, information will be reviewed again with the individual. If after review the subject cannot verbalize understanding, he/she will not be enrolled in the study. Amish liaisons may provide explanation in PA Dutch if necessary to aid understanding.

8 \* Describe the consideration for ongoing consent:

This study involves one time sample collection and follow up survey or interview. At the time of survey or interview, participants will be reminded the purpose and voluntary nature of the research. They will be reminded that they may decline or withdraw from participation without any negative consequences.

ID: VIEW4E1C661D0AC00  
Name: v2\_Informed Consent Process

HP-00081981

Waiver of Documentation of Consent\_V2

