**1 \* Describe the purpose, specific aims, or objectives of this research. State the hypothesis to be tested:**

This study will evaluate the ethical, legal and social impacts of patients receiving genetic results and will assess whether providing free genetic testing in a very convenient manner (in-home, saliva collection) will improve uptake of cascade testing.

The objectives of the protocol are to: (Aim 1) evaluate the uptake of cascade screening and preventative therapies before and after the implementation of a simplified screening process and (Aim 2) assess proband and family member perspectives about the return of research results and cascade screening for the KCNQ1 Thr224Met variant. We will conduct a mixed methods study in the Old Order Amish community where the KCNQ1 variant is enriched over 100,000-fold compared to other populations. The intervention will offer free, saliva-based genetic testing for family members of probands. The rate of uptake of testing and preventative therapy will be compared before (i.e. when 'traditional' \$50 blood-based testing was available to family members) and after the intervention is implemented (i.e. when 'simplified' free, in-home, saliva-based testing was available).

Aim 1 - The primary outcome is the rate of uptake of cascade screening before ('traditional') versus after ('simplified') the intervention. The secondary outcomes include: extent of disclosure of genotype results to family members before and after the intervention, proportion of informed relatives who get screened before and after the intervention, and the uptake of appropriate preventative care (e.g. seeing a cardiologist and/or taking beta-blocker). The tertiary outcomes are demographic characteristics associated with uptake of cascade screening or uptake of preventative therapy.

Aim 2 - We will also assess qualitative themes surrounding the return of results process and cascade screening using interviews.

**2 \* Discuss the research design including but not limited to such issues as: probability of group assignment, potential for subject to be randomized to placebo group, use of control subjects, etc.:**

This study will use mixed methods to evaluate the rate of uptake and impact of cascade screening and preventative therapies for carriers of the KCNQ1 mutation before and after our intervention. Our intervention will offer free, saliva-based cascade screening for first-degree family members of probands.

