To date, 88 individuals have participated in a return of results study (ROR) for clinical confirmation of the mutation, collection of clinical information, genetic counseling, and recommendations for treatment. Genetic counseling included recommendations for all first degree relatives (who are at 50% risk of having the KCNQ1 mutation) to undergo genetic screening (cascade testing). This testing would involve going to the Clinic for Special Children and obtaining the genetic test via a blood sample for \$50 per test.

Cascade testing is considered to be a highly efficient procedure for identifying additional mutation carriers who might be helped through a preventive intervention. Despite the very clear potential clinical benefit of cascade testing, uptake has traditionally been low, particularly in the United States where active screening (i.e. direct contact of relatives) is not allowed due to privacy laws.

Understanding the impact of returning these results and initiating cascade screening of family members is critical for developing best practices and optimizing the processes. Most cascade screening studies to date have been conducted outside the United States where different laws exist regarding contacting family members. Therefore, our study will attempt to address a gap in knowledge regarding whether overcoming physical and financial barriers will improve uptake of cascade screening.

**4 \*Provide the scientific or scholarly background, rationale, and significance of the research and how it will add to existing knowledge:**

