In the invitation letter, family members will be asked to take part in a study involving screening for the KCNQ1 variant, including any or all of the following: provide a saliva sample to check for the KCNQ1 genetic variant at no cost to them, complete a questionnaire about their attitudes and experience with genetic testing, and possibly take part in an in-person interview. They will be instructed to return a response form or call the Amish Research clinic if they are interested in participating in the study.

Family members who indicate, by returning the response card or by phone call, that they are interested in participating in the free genetic testing will be visited in their home by a study team member and an Amish liaison. Initial interactions are described in the Recruitment Section. For those who are interested in participating, informed consent will be obtained from adults and parents of minor children. Written assent will be obtained from minors aged 13-17; verbal assent will be obtained from children 7-12 years of age. Consent and assent will be obtained prior to any study procedures are performed. The informed consent process is detailed in the Consent Section of this application. Participants/parents will be asked to complete a questionnaire including demographics, medical and family history, and medications (uploaded in.

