## Recruitment

1 \* Describe plans for recruitment, including the identification of potential participants (or acquisition of charts/records/samples) and initial interactions with them: (If this study involves the VA please list all sites at which recruitment will take place.):  
Individuals who participated in the KCNQ1 ROR study (probands) and their first degree blood-related family members will be invited to participate. First degree family members of identified carriers will also be eligible for testing.

All probands who underwent the return of results process (n=88 to date) will be mailed an information / consent letter and response form (uploaded in Informed Consent Section), a questionnaire about their attitudes and experience with genetic testing (uploaded to Surveys Section), and a sample family invitation letter (uploaded below). These participants all agreed to recontact during the consent process for the study their KCNQ1 ROR was conducted under (see Retrospective Data Section). In the information/consent letter, probands will be asked to complete and return the questionnaire as an indication that they agree to join the study. They will be informed that they may be asked to participate in an in-person interview. The letter will also ask if we can invite their adult first-degree family members who live locally to take part in the study, whether or not the proband participates. They will be given the option to enroll their minor children (with appropriate consent and assent) in the free cascade testing portion of the study. The proband will complete and return the response form to indicate whether they agree to contact of family members.

With the proband's permission, the family invitation letter will be mailed to the first-degree family members of the proband using information from the 2009 Fisher Book and 2018 Address book of the Lancaster County Amish. At the proband's request, copies of the family invitation letter will, instead, be mailed to the proband so they can hand deliver them to family members of their choosing. The family invitation letter will explain our intervention offering free, mail-in, saliva testing of first degree family members.

2 \* Describe measures that will be implemented to avoid participant coercion or undue influence (if not applicable to the study, enter "N/A"):

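### Home visits to relatives who have not replied are allowed in one section without any rule, and the tests they produce are counted as uptake of free, convenient testing

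*Combined protocol and SAP*

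**What the plan says.** Study Procedures (item 1) describes an opt-in route. The invitation letter tells relatives to "return a response form or call the Amish Research clinic if they are interested in participating in the study". Those who indicate by card or phone "that they are interested in participating in the free genetic testing will be visited in their home by a study team member", accompanied by a liaison. No other trigger for a visit is given there.

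Informed Consent Process (item 2) says relatives are visited at home after the clinic staff receive their "response card expressing interest in testing, or possibly if no response is received". It does not say who among the non-responders is visited, at what point, how many times, or who decides.

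The purpose and aims (Justification, Objective, & Research Design, item 1) define the simplified period as the time "when 'simplified' free, in-home, saliva-based testing was available". Under the traditional approach (item 3 of the same section), testing meant "going to the Clinic for Special Children and obtaining the genetic test via a blood sample" for $50, and no visit to relatives by study staff is described. Recruitment (item 1) says the family letter explains an intervention "offering free, mail-in, saliva testing of first degree family members", which does not match in-home collection.

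The primary numerator is the number of persons screened, taken from charts (Sample Size and Data Analysis, item 2; SAP B1.1). Neither text splits it by how the relative came to be tested.

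**The concern.** The protocol wants to learn how far cost and ease of testing change uptake (Justification, Objective, & Research Design, item 2). Collection at home is part of that intervention. A nurse and a liaison arriving at the home of someone who did not answer the letter is something else, namely active solicitation in person. The protocol itself treats direct contact as relevant to uptake: item 3 links low uptake in the United States to privacy laws that do not allow direct contact of relatives.

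If such visits take place, they add tests to the simplified period through a route with no described counterpart in the traditional period. Because their use is left open, the primary result would partly reflect how much visiting the staff chose to do. A clinic that offered a free saliva test and a letter, without the visits, could not expect the same uptake. If the route is not recorded at the time, it may not be recoverable later.

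**Working it through.** **Step 1. The texts side by side.**

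- Trigger for a visit: a positive response (Study Procedures); a positive response or possibly none (Informed Consent Process).
- Rule for non-responders: none in either section. Study Procedures refers to Recruitment for initial interactions, but Recruitment gives no such rule.
- Route to each test in the analysis: not recorded or used in Sample Size and Data Analysis or in SAP B1.1.
- Handling of other explanations: the Lay Summary (Aim 2) accepts that a second reminder, or another feature of the design, could explain uptake, and assigns the question to interviews. Visits to non-responders are not named. The 45 family interviews are sampled purposively, 15 per category, so they cannot estimate what share of tests followed such visits.

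**Step 2. The plan's own example** (Sample Size and Data Analysis, item 1; SAP A1). Before: 0.03 × 500 = 15. Remaining: 500 − 15 = 485. After: 0.18 × 485 = 87.3, stated as 87. Then 87/485 = 17.9%, and 17.9% − 3.0% = 14.9 points, which is the plan's 15-point improvement. The example reproduces. No alpha or power is given, so no power formula applies.

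**Step 3. How much visiting would reach 87?** The documents give neither the uptake after a positive response, nor the share of other relatives visited, nor the share of those who accept. The values below are assumptions that show the range. Let *r* be the share of the 485 tested after a positive response, *v* the share of the remaining relatives visited unsolicited, and *a* the share of those visited who are tested. Relatives who may not be approached count as not visited. The product needed is *v* × *a* = (87 − 485*r*) / (485 − 485*r*).

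| *r* | Tested after a response | Short of 87 | Remaining | *v* × *a* needed |
|---|---|---|---|---|
| 3% | 14.55 | 72.45 | 470.45 | 15.4% |
| 5% | 24.25 | 62.75 | 460.75 | 13.6% |
| 10% | 48.5 | 38.5 | 436.5 | 8.8% |
| 15% | 72.75 | 14.25 | 412.25 | 3.5% |

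**Step 4. Two cases.**

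- *r* = 10%, half of the rest visited, 20% accepting: 48.5 + 436.5 × 0.5 × 0.2 = 92.15, or 19.0% of 485. Response-initiated uptake of 10% is below the mark and the total is above it.
- *r* = 3%, a quarter visited, 10% accepting: 14.55 + 470.45 × 0.25 × 0.1 = 26.3, or 5.4%. Both figures are well below the mark.

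**The case against.** The two sections can be read together. Study Procedures says that interested relatives will be visited; it does not say that nobody else will be. A reader might infer a ban on other visits, but the restriction is only implied, by the opt-in instruction and the absence of another route. Informed Consent Process may simply add a second route. That stands, but the second route still has no rule.

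The primary outcome compares uptake before and after a bundled programme, in a self-described pilot that disclaims a statistical comparison, and home visits belong to the bundle. This also stands, and it narrows the point to the unsolicited approach. It does not remove the point, because the protocol goes on to attribute uptake to cost and ease. The Lay Summary does acknowledge the general problem, but the interviews cannot supply a number.

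Three stronger readings are not supported:

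- **Mail-in testing as a staff option.** A reader might see a third intensity of intervention. The phrase occurs once, in describing the family letter, and the procedures describe collection at home. It is a separate wording inconsistency.
- **A calculated bias.** SAP B1.3 expects about 60% of surveys back. A reader might take 40% of 485 = 194 as non-responders and conclude that 72.75/194 = 37.5% acceptance would supply all 15 points (0.15 × 485 = 72.75). But 60% is a survey return rate, 485 belongs to a hypothetical example, and the sum assumes that every non-responder is visited. The pool that could be visited is smaller: the proband's permission is required (Eligibility), letters go to relatives who live locally (Study Procedures), and the proband's minor children at home enter through the proband.
- **Response-initiated uptake as the true effect of free, convenient testing.** Those tests also follow the new letter, which acts as a reminder. Excluding visit-prompted tests also removes relatives who might have replied later.

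**Conclusion.** The point holds as a gap in the contact rule and in the data needed to interpret the primary outcome. The sections differ on what triggers a home visit, visits to non-responders are left to discretion, and their tests would be pooled with the rest and read as an effect of cost and ease.

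The documents do not allow the size to be computed. Under the assumptions shown, such visits would have to yield tests in anything from 3.5% to 15.4% of the remaining relatives to reach the plan's 87 of 485, so their influence could be negligible or could decide the conclusion. The documents do not show that such visits will be common, or that the result will be biased by any given amount. The conclusion rests on the texts as they stand and on the intended attribution to cost and ease. It does not rest on any forecast of response or acceptance.

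**What to change.** 1. Reconcile Study Procedures and Informed Consent Process to one stated contact rule for all relatives whom the proband has permitted the study to contact: whether non-responders are visited and, if so, which, when and how often.
2. Change the mail-in wording in Recruitment to match in-home collection, or explain it.
3. Record for each test whether it followed the relative's own response, the proband's enrolment of a minor child, or an unsolicited visit.
4. In SAP B1.1, report primary uptake in total and by route, with a sensitivity analysis that excludes tests first prompted by an unsolicited visit. If the two figures fall on different sides of the 15-point mark, limit the claim that free, convenient testing produced the improvement.

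The cost is some protocol wording and one field in the visit log. The sensitivity figure may be lower than the total. It is conservative, because some visited relatives might have responded later, so it belongs beside the total and should not replace it.
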